16.1 Study Discontinuation

Subjects may be discontinued at any time from the study for any of the following reasons:

- Grade ≥ 3 skin toxicity develops
- An AE occurs that, in the opinion of the Investigator, makes it unsafe for the subject to continue in the study, included laboratory test abnormalities evaluation
- Lack of compliance of the subject to the study treatment or assessments
- The subject is lost to follow-up
- The subject dies
- The subject withdraws consent

- The Investigator, for any reason, terminates the entire study, or terminates the study for that subject or the attending physician requests that the subject be withdrawn for any medical reason
- The Sponsor or the Regulatory Authority or the Ethics Committee, for any reason, terminates the entire study or terminates the study for this site or this particular subject.

If a subject is discontinued from the study, the Investigator will, as far as possible, complete the end of study visit (visit 9 or 10) CRF pages. The Investigator should try to ascertain the reason(s) for withdrawal, while fully respecting the subject's rights.

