5.2 Secondary Objectives

The secondary objectives of this clinical investigation are:

1. to evaluate the median time to G2 radiation dermatitis development according to CTCAE
2. to evaluate the proportion of patients without G2 radiation dermatitis at week 6 for both cancer sites, at week 7 for head & neck cancer and two weeks after the last radiation for both cancer sites .
3. to evaluate the worst skin toxicity during treatment and until 2 weeks after the last radiation, according to CTCAE
4. to evaluate changes in skin erythema and pigmentation and trans-epidermal water loss (TEWL)
5. to evaluate the mean and worst score of Patient Reported Outcome (PRO) with Skindex-16 questionnaire performed weekly
6. to evaluate the compliance to experimental treatment use
7. to evaluate the patient global satisfaction with treatment as assessed by Likert scale.

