6.2.1.4 Study product accountability and compliance

The Investigator is responsible for ensuring the accountability of the study product.

Accountability records will include:

- confirmation of product delivery and receipt to/at the clinical site
- records concerning the product delivery to each subject and the return from each subject
- the return to the Sponsor or alternative disposition of unused products.

The Investigator should maintain records that adequately document:

- that the subjects were provided with the doses specified by the clinical investigation plan/amendment(s)
- that all products provided by the Sponsor were fully reconciled.

Unused products must not be discarded or used for any purpose other than the present clinical investigation.

Products that has been allocated to one subject must not be re-dispensed to a different subject.

Subjects will be reminded of the importance of strictly complying with the instructions received from the Investigator and to return all unused treatment or empty bottles to the Investigator.

The Monitor, at monitoring visits, will verify the products accountability and will check all products returned by the subjects (unused, used and partially used) before arranging for their return to the Sponsor.

Compliance to the treatment will be checked by the Investigators when the subjects are bringing back to the Site the used/unused products. A cross check will be done with patient's diary information.

The treatment compliance will be then evaluated by weighing the bottles before return to the Sponsor.

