7.2 Definition of Study Populations for Analysis

The study will be analyzed using an Intent-to-Treat (ITT) approach. All randomized patients receiving at least a treatment dose and having at least one post-randomization efficacy evaluation will be included in the ITT population for efficacy analysis. All randomized patients receiving at least a treatment dose will be included in the safety analysis.

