7.3.1 Missing Data

Missing values will not be replaced unless specified otherwise. Missing safety data will not be replaced.

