#### **9.1.3 Treatment Compliance**

The compliance with the treatment will be assessed through a diary where the patient will record the daily product applications and through the difference in weight of tubes when delivered to patient and when returned by the patient. The consistency between the two assessments will be checked (see paragraph 11.3).

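### Discontinuing patients from the study for non-compliance with treatment can lose week-5 grades mainly from the Xonrid arm, and the compliance denominator can overstate adherence

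*Protocol*

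**What the plan says.** Protocol 16.1 opens its list with "Subjects may be discontinued at any time from the study for any of the following reasons", and one of the reasons is "Lack of compliance of the subject to the study treatment or assessments". The exit is from the study and no compliance threshold is given. For a patient who leaves, "the Investigator will, as far as possible, complete the end of study visit (visit 9 or 10) CRF pages". Nothing asks for the week-5 grade.

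The compliance objective (Protocol 5.2) is "to evaluate the compliance to experimental treatment use". The defined measures all concern the gel:
- a diary of product applications, and product use assessed "through the difference in weight of tubes when delivered to patient and when returned by the patient" (SAP 9.1.3);
- bottle weights, for which Protocol 6.2.1.4 says "The treatment compliance will be then evaluated by weighing the bottles before return to the Sponsor".

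Standard-of-care measures are recommended to everyone (Protocol 6.2.2), but no adherence measure is defined for them.

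On analysis, Protocol 7.2 states "The study will be analyzed using an Intent-to-Treat (ITT) approach" and Protocol 7.3.1 states "Missing values will not be replaced unless specified otherwise". SAP 8.1 and 9.1.4 repeat both. SAP 10.2 adds that patients with critical deviations are left out of the analysis, without defining critical. SAP 11.3 computes compliance as applications reported divided by three times the days actually on treatment.

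**The concern.** Only Group A has a product whose use is recorded. A Group A patient who applies the gel poorly can be taken out of the study on that ground. A Group B patient in the same skin condition has no recorded product use on which to be removed. If the Group A patient leaves before week 5, the plan neither seeks the primary outcome nor replaces it. The patient can remain in the ITT set by definition and still contribute nothing to the week-5 chi-square test.

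If poor compliance goes with worsening skin, the patients lost would tend to be those heading for G2. The week-5 comparison would then favour Xonrid with no device effect. The undefined exclusion in SAP 10.2 could remove non-compliant patients even where a grade exists.

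Compliance itself is also affected. Once a poor complier leaves, the applications still scheduled for that patient drop out of the denominator.

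**Working it through.** **1. The plan's own sample size.** Inputs from Protocol 7.1: 38.2% and 82.9% without G2 at week 5, two-sided 0.05, 80% power, chi-square test. The mean proportion is (0.382 + 0.829)/2 = 0.6055.

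n = [1.96 × √(2 × 0.6055 × 0.3945) + 0.8416 × √(0.382 × 0.618 + 0.829 × 0.171)]² / 0.447² = (1.355 + 0.517)² / 0.1998 ≈ 17.5, so 18 per group. With 10% dropout, 18/0.9 = 20. The stated figures reproduce. SAP 9.1 analyses each cancer site separately, so each comparison is 20 v 20.

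**2. When non-compliance can be seen.** Week 5 is visit 7. Product comes back at visit 8 (breast, week 6) or visit 9 (head and neck, week 7), and again at the final visit (Protocol 6.4.1). Weighing therefore comes after week 5. Only the diary, checked for completeness at each visit, could prompt an earlier exit.

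**3. Effect on power.** With losses in Group A only and the planned effect, approximate power per site is 85.3% with none lost, 83.1% with 2, 80.3% with 4 and 78.7% with 5. Power is not the main problem.

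**4. Effect on bias.** Assume no device effect (38.2% in both arms) and that each would-be G2 patient in Group A is lost before week 5 with probability q.
- Expected number lost = 20 × 0.618 × q = 12.36q.
- Expected observed Group A rate = 0.382 / [0.382 + 0.618(1 − q)].
- Rejection probabilities come from exact enumeration of the uncorrected chi-square test.

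| q (assumed) | Expected lost | Group A observed | Significant favouring Xonrid | Two-sided type I error |
|---|---|---|---|---|
| 0 | 0 | 38.2% | 2.5% | 5.0% |
| 0.10 | 1.2 | 40.7% | 3.6% | 5.3% |
| 0.16 | 2.0 | 42.4% | 4.4% | 5.7% |
| 0.20 | 2.5 | 43.6% | 5.1% | 6.2% |
| 0.30 | 3.7 | 46.9% | 7.5% | 8.2% |

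The row q = 0.16 corresponds to the plan's whole dropout allowance (2 of 20) being selective loss of this kind. If loss is unrelated to outcome, there is no bias and only precision suffers.

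**5. Effect on the compliance figure.** Assumed illustration in 20 breast patients: 18 complete with 95% of applications, and 2 stop at day 21 of 56 having made half of theirs.
- SAP formula: each early leaver scores 50%, so the mean is (18 × 95 + 2 × 50)/20 = 90.5%.
- Against scheduled applications: each early leaver scores 50 × 21/56 = 18.75%, so the mean is (18 × 95 + 2 × 18.75)/20 = 87.4%.
- Completers only: 95%.

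**The case against.** The strongest case on the other side has five parts.

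- **The rule is permissive.** Its assessments limb covers both arms, and the flow-charts do not restrict the diary to one arm. Some Group B departures, such as using a metallic topical product, could surface in the concomitant-medication review. This stands, and it rules out saying that outcomes are necessarily lost, or lost from one arm only. It does not remove the asymmetry of the treatment limb, whose only defined measures concern the gel.
- **Early detection is limited.** Bottle weights cannot trigger an exit before week 5, and the diary check is for completeness. This stands and narrows the route to the diary.
- **Losses may be smaller.** The larger assumed losses (2.5 and 3.7 of 20) exceed the plan's 10% allowance for dropout from every cause. At 1.2 lost the favourable error is only 3.6%. This stands.
- **Some lost patients may already count.** SAP 14.2 tabulates patients who reached or did not reach G2 at week 5. On a cumulative reading, a patient graded G2 before leaving is already a failure. The bias then comes only from patients who leave before any G2 grade. This stands on that reading, although the endpoint text can also be read as the grade at the week-5 visit.
- **Discontinuations are already reported.** The SAP plans dropout tables and a listing of discontinued patients. These describe the losses but do not recover the grades.

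A reader might also infer that compliance is evaluated only among compliers. The documents do not support that. SAP 11.5 assigns compliance to the ITT population, and an early leaver with a dose and a later efficacy assessment stays in it. The illustration shows the difference: 90.5% under the SAP formula against 95% for completers only.

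**Conclusion.** The concern holds as a risk of differential missing week-5 outcomes, mainly in Group A, that the plan creates and does not guard against. Three features produce it together: an exit from the study for treatment non-compliance that is measurable only for the gel, no week-5 grade required after exit, and no replacement of missing values. This is at odds with the stated ITT approach.

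The size depends on assumptions, because the documents give no discontinuation figures by arm. If the patients lost are would-be G2 cases, about 1.2, 2.5 or 3.7 lost from 20 moves the chance of a significant result favouring Xonrid from 2.5% to 3.6%, 5.1% or 7.5%. Losses within the 10% dropout allowance keep it at or below about 4.4%. The sample size is not at fault.

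On compliance, the supported statement is that the days-on-treatment denominator can overstate adherence when patients leave early: 90.5% against 87.4% in the illustration.

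**What to change.** **Protocol 16.1.** Separate non-compliance with study treatment from leaving the study. Such patients, in either arm, continue weekly grading, including week 5, and are analysed as randomised. This concerns follow-up and data only; it changes no clinical decision about treatment.

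**SAP.**
- State that non-compliance with treatment is not a critical deviation under 10.2, so these patients stay in the primary analysis.
- Add a sensitivity analysis for missing week-5 grades, for example counting a missing grade as G2 reached. If 8 of 20 in Group A are truly G2-free and two would-be G2 patients are lost, the available-case rate is 8/18 = 44.4%, and this rule returns it to 8/20 = 40%. It can also penalise the arm with more losses (15/18 = 83.3% would become 15/20 = 75%), so it belongs beside the main analysis, not in place of it.
- Report compliance against scheduled applications as well as against days on treatment.

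**Cost.** One bullet in the protocol and a few lines in the SAP. At week 5 patients in both sites are still attending for weekday radiotherapy, so the grade needs no extra attendance. The downside is a slightly diluted Xonrid estimate, which is what an ITT analysis accepts. SAP Sections 2 and 7 describe the 80 patients as already enrolled. If so, only the SAP changes can still be made.

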16.2 Study Interruption

The Sponsor may consider study closure at the clinical site if the following occurs:

- serious and/or persistent non-compliance with the Clinical Investigation Plan
- inadequate collaboration of site personnel with CRO/Sponsor
- administrative reasons
- non-compliance with GCP, SOPs or regulatory requirements
- lack of confidentiality and/or non-compliance with the contract spread with the Sponsor.

17. Publication policy

All information obtained as a result of the study will be regarded as confidential.

The results of the clinical study will be documented in an integrated clinical study report according to ISO 14155.

The Sponsor and the Investigator(s) agree that no publications presenting or discussing data and/or results from clinical study sponsored by Helsinn Healthcare SA will take place until the participating center has completed the study, the data have been interpreted, and the final report has been issued.

As a rule, the Sponsor is free to use the data collected in the sponsored study for world-wide scientific product documentation, and for publication.

In general, the Sponsor has no objections if the Investigator publishes the results of the study sponsored by Helsinn Healthcare SA. However, the Investigator is requested to provide the Sponsor with a copy of the manuscript for review before submitting it to the publisher with a cover letter informing the Sponsor about the intention to publish the study results. When permission for presentation or for publication is granted, Investigators, prior to submission of a manuscript or abstract to the publisher, shall forward a copy of said manuscript or abstract to the Sponsor who shall have 45 days to request any reasonable amendment thereto, which shall be taken into due account and consideration by the Investigator.

The Sponsor is entitled to include as authors of the publication all Sponsor's personnel who contributed substantially to the theoretical or experimental work and also to take part in the decision that establishes the order in which the authors' names will be given. Costs for publication must be regulated by written agreement between the parties.

Phase of the study	Screening	RT & treatment start	RT (expected 33-35 sessions)						RT end	2 weeks treatment without RT
Visit number	1	2	3	4	5	6	7	8	9	10
Week	-	0	1	2	3	4	5	6	7	9
Time (Days) ± 2 days	-3 to 0	1	7	14	21	28	35	42	49	63
Informed consent signature	X									
Inclusion/Exclusion criteria	X	X								
Patient randomization		X								
Socio-demographic data	X									
Medical and surgical history collection	X									
Physical examination	X	X	X	X	X	X	X	X	X	X
Concomitant medications and therapies	X	X	X	X	X	X	X	X	X	X
ECOG performance status	X									
Erythema assessment	X	X	X	X	X	X	X	X	X	X
Skindex-16 questionnaire	X	X	X	X	X	X	X	X	X	X
Spettrophotometry & TEWL		X	X	X	X	X	X	X	X	X
Study treatment dispensation to patient		X							X	
Study treatment return and accountability									X	X
Patient diary dispensation		X							X	
Patient diary collection									X	X
Patient Global Satisfaction score									X	X
Adverse events		X	X	X	X	X	X	X	X	X

Study Flow-Chart for breast cancer subjects

Phase of the study	Screening	RT & treatment start	RT (expected 30 sessions)						RT end	2 weeks treatment without RT
Visit number	1	2	3	4	5	6	7	8		9
Week	-	0	1	2	3	4	5	6		8
Time (Days) ± 2 days	-3 to 0	1	7	14	21	28	35	42		56
Informed consent signature	X									
Inclusion/Exclusion criteria	X	X								
Patient randomization		X								
Socio-demographic data	X									
Medical and surgical history collection	X									
Physical examination	X	X	X	X	X	X	X	X		X
Concomitant medications and therapies	X	X	X	X	X	X	X	X		X
ECOG performance status	X									
Erythema assessment	X	X	X	X	X	X	X	X		X
Skindex-16 questionnaire	X	X	X	X	X	X	X	X		X
S Spettrophotometry & TEWL		X	X	X	X	X	X	X		X
Study treatment dispensation to patient		X							X	
Study treatment return and accountability									X	X
Patient diary dispensation		X							X	
Patient diary collection									X	X
Patient Global Satisfaction score									X	X
Adverse events		X	X	X	X	X	X	X		X

Appendix 3: SKINDEX-16 Questionnaire

QUESTIONARIO DERMATOLOGICO

Questo questionario riguarda il problema di pelle che le ha dato più fastidio negli ultimi 7 giorni.

Skindex-16
©MMChren,1997

**QUESTE DOMANDE RIGUARDANO IL PROBLEMA DI PELLE CHE LE HA DATO
PIÙ FASTIDIO NEGLI ULTIMI 7 GIORNI**

**Negli ultimi 7 giorni, quanto spesso le
ha/hanno dato fastidio:**

	Non mi ha mai dato fastidio							Mi ha sempre dato fastidio						
	↓	•	•	•	•	•	•	↓	•	•	•	•	•	•
1. Il prurito dovuto al suo problema di pelle	 0	 1	 2	 3	 4	 5	 6							
2. Il bruciore o il pizzicore dovuti al suo problema di pelle.	 0	 1	 2	 3	 4	 5	 6							
3. Il dolore dovuto al suo problema di pelle	 0	 1	 2	 3	 4	 5	 6							
4. L'irritazione dovuta al suo problema di pelle	 0	 1	 2	 3	 4	 5	 6							
5. La persistenza/ricomparsa del suo problema di pelle .	 0	 1	 2	 3	 4	 5	 6							
6. La preoccupazione per via del suo problema di pelle (Per es. che si possa estendere, peggiorare, lasciare segni, essere imprevedibile, ecc.)	 0	 1	 2	 3	 4	 5	 6							
7. L'aspetto del suo problema di pelle	 0	 1	 2	 3	 4	 5	 6							
8. La frustrazione per via del suo problema di pelle . . .	 0	 1	 2	 3	 4	 5	 6							
9. L'imbarazzo per via del suo problema di pelle	 0	 1	 2	 3	 4	 5	 6							
10. Essere seccato/a per via del suo problema di pelle . .	 0	 1	 2	 3	 4	 5	 6							
11. Sentirsi depresso/a per via del suo problema di pelle	 0	 1	 2	 3	 4	 5	 6							
12. Le conseguenze del suo problema di pelle sui suoi rapporti con gli altri (Per es.: rapporti con familiari, amici, rapporti intimi, ecc.)	 0	 1	 2	 3	 4	 5	 6							
13. Le conseguenze del suo problema di pelle sul suo desiderio di stare con gli altri.	 0	 1	 2	 3	 4	 5	 6							
14. La difficoltà di manifestare il suo affetto a causa del suo problema di pelle	 0	 1	 2	 3	 4	 5	 6							
15. Le conseguenze del suo problema di pelle sulle sue attività quotidiane	 0	 1	 2	 3	 4	 5	 6							
16. La difficoltà di lavorare o fare quello che le piace a causa del suo problema di pelle	 0	 1	 2	 3	 4	 5	 6							

Ha risposto a tutte le domande? Sì No

Appendix 4: Helsinki Declaration

WORLD MEDICAL ASSOCIATION DECLARATION OF HELSINKI Ethical Principles for Medical Research Involving Human Subjects

Adopted by the 18th WMA General Assembly, Helsinki, Finland, June 1964
and amended by the:

29th WMA General Assembly, Tokyo, Japan, October 1975

35th WMA General Assembly, Venice, Italy, October 1983

41st WMA General Assembly, Hong Kong, September 1989

48th WMA General Assembly, Somerset West, Republic of South Africa, October 1996

52nd WMA General Assembly, Edinburgh, Scotland, October 2000

53rd WMA General Assembly, Washington DC, USA, October 2002 (Note of Clarification added)

55th WMA General Assembly, Tokyo, Japan, October 2004 (Note of Clarification added)

59th WMA General Assembly, Seoul, Republic of Korea, October 2008

64th WMA General Assembly, Fortaleza, Brazil, October 2013

Preamble

1. The World Medical Association (WMA) has developed the Declaration of Helsinki as a statement of ethical principles for medical research involving human subjects, including research on identifiable human material and data.

The Declaration is intended to be read as a whole and each of its constituent paragraphs should be applied with consideration of all other relevant paragraphs.

2. Consistent with the mandate of the WMA, the Declaration is addressed primarily to physicians. The WMA encourages others who are involved in medical research involving human subjects to adopt these principles.

General Principles

3. The Declaration of Geneva of the WMA binds the physician with the words, "The health of my patient will be my first consideration," and the International Code of Medical Ethics declares that, "A physician shall act in the patient's best interest when providing medical care."

4. It is the duty of the physician to promote and safeguard the health, well-being and rights of patients, including those who are involved in medical research. The physician's knowledge and conscience are dedicated to the fulfilment of this duty.

5. Medical progress is based on research that ultimately must include studies involving human subjects.

6. The primary purpose of medical research involving human subjects is to understand the causes, development and effects of diseases and improve preventive, diagnostic and therapeutic interventions

(methods, procedures and treatments). Even the best proven interventions must be evaluated continually through research for their safety, effectiveness, efficiency, accessibility and quality.

7. Medical research is subject to ethical standards that promote and ensure respect for all human subjects and protect their health and rights.

8. While the primary purpose of medical research is to generate new knowledge, this goal can never take precedence over the rights and interests of individual research subjects.

9. It is the duty of physicians who are involved in medical research to protect the life, health, dignity, integrity, right to self-determination, privacy, and confidentiality of personal information of research subjects. The responsibility for the protection of research subjects must always rest with the physician or other health care professionals and never with the research subjects, even though they have given consent.

10. Physicians must consider the ethical, legal and regulatory norms and standards for research involving human subjects in their own countries as well as applicable international norms and standards. No national or international ethical, legal or regulatory requirement should reduce or eliminate any of the protections for research subjects set forth in this Declaration.

11. Medical research should be conducted in a manner that minimises possible harm to the environment.

12. Medical research involving human subjects must be conducted only by individuals with the appropriate ethics and scientific education, training and qualifications. Research on patients or healthy volunteers requires the supervision of a competent and appropriately qualified physician or other health care professional.

13. Groups that are underrepresented in medical research should be provided appropriate access to participation in research.

14. Physicians who combine medical research with medical care should involve their patients in research only to the extent that this is justified by its potential preventive, diagnostic or therapeutic value and if the physician has good reason to believe that participation in the research study will not adversely affect the health of the patients who serve as research subjects.

15. Appropriate compensation and treatment for subjects who are harmed as a result of participating in research must be ensured.

Risks, Burdens and Benefits

16. In medical practice and in medical research, most interventions involve risks and burdens.

Medical research involving human subjects may only be conducted if the importance of the objective outweighs the risks and burdens to the research subjects.

17. All medical research involving human subjects must be preceded by careful assessment of predictable risks and burdens to the individuals and groups involved in the research in comparison with

foreseeable benefits to them and to other individuals or groups affected by the condition under investigation.

Measures to minimise the risks must be implemented. The risks must be continuously monitored, assessed and documented by the researcher.

18. Physicians may not be involved in a research study involving human subjects unless they are confident that the risks have been adequately assessed and can be satisfactorily managed.

When the risks are found to outweigh the potential benefits or when there is conclusive proof of definitive outcomes, physicians must assess whether to continue, modify or immediately stop the study.

Vulnerable Groups and Individuals

19. Some groups and individuals are particularly vulnerable and may have an increased likelihood of being wronged or of incurring additional harm.

All vulnerable groups and individuals should receive specifically considered protection.

20. Medical research with a vulnerable group is only justified if the research is responsive to the health needs or priorities of this group and the research cannot be carried out in a non-vulnerable group. In addition, this group should stand to benefit from the knowledge, practices or interventions that result from the research.

Scientific Requirements and Research Protocols

21. Medical research involving human subjects must conform to generally accepted scientific principles, be based on a thorough knowledge of the scientific literature, other relevant sources of information, and adequate laboratory and, as appropriate, animal experimentation. The welfare of animals used for research must be respected.

22. The design and performance of each research study involving human subjects must be clearly described and justified in a research protocol.

The protocol should contain a statement of the ethical considerations involved and should indicate how the principles in this Declaration have been addressed. The protocol should include information regarding funding, sponsors, institutional affiliations, potential conflicts of interest, incentives for subjects and information regarding provisions for treating and/or compensating subjects who are harmed as a consequence of participation in the research study.

In clinical trials, the protocol must also describe appropriate arrangements for post-trial provisions.

Research Ethics Committees

23. The research protocol must be submitted for consideration, comment, guidance and approval to the concerned research ethics committee before the study begins. This committee must be transparent in its functioning, must be independent of the researcher, the sponsor and any other undue influence

and must be duly qualified. It must take into consideration the laws and regulations of the country or countries in which the research is to be performed as well as applicable international norms and standards but these must not be allowed to reduce or eliminate any of the protections for research subjects set forth in this Declaration.

The committee must have the right to monitor ongoing studies. The researcher must provide monitoring information to the committee, especially information about any serious adverse events. No amendment to the protocol may be made without consideration and approval by the committee. After the end of the study, the researchers must submit a final report to the committee containing a summary of the study's findings and conclusions.

Privacy and Confidentiality

24. Every precaution must be taken to protect the privacy of research subjects and the confidentiality of their personal information.

Informed Consent

25. Participation by individuals capable of giving informed consent as subjects in medical research must be voluntary. Although it may be appropriate to consult family members or community leaders, no individual capable of giving informed consent may be enrolled in a research study unless he or she freely agrees.

26. In medical research involving human subjects capable of giving informed consent, each potential subject must be adequately informed of the aims, methods, sources of funding, any possible conflicts of interest, institutional affiliations of the researcher, the anticipated benefits and potential risks of the study and the discomfort it may entail, post-study provisions and any other relevant aspects of the study. The potential subject must be informed of the right to refuse to participate in the study or to withdraw consent to participate at any time without reprisal. Special attention should be given to the specific information needs of individual potential subjects as well as to the methods used to deliver the information.

After ensuring that the potential subject has understood the information, the physician or another appropriately qualified individual must then seek the potential subject's freely-given informed consent, preferably in writing. If the consent cannot be expressed in writing, the non-written consent must be formally documented and witnessed.

All medical research subjects should be given the option of being informed about the general outcome and results of the study.

27. When seeking informed consent for participation in a research study the physician must be particularly cautious if the potential subject is in a dependent relationship with the physician or may consent under duress. In such situations the informed consent must be sought by an appropriately qualified individual who is completely independent of this relationship.

28. For a potential research subject who is incapable of giving informed consent, the physician must seek informed consent from the legally authorised representative. These individuals must not be included in a research study that has no likelihood of benefit for them unless it is intended to promote

the health of the group represented by the potential subject, the research cannot instead be performed with persons capable of providing informed consent, and the research entails only minimal risk and minimal burden.

29. When a potential research subject who is deemed incapable of giving informed consent is able to give assent to decisions about participation in research, the physician must seek that assent in addition to the consent of the legally authorised representative. The potential subject's dissent should be respected.

30. Research involving subjects who are physically or mentally incapable of giving consent, for example, unconscious patients, may be done only if the physical or mental condition that prevents giving informed consent is a necessary characteristic of the research group. In such circumstances the physician must seek informed consent from the legally authorised representative. If no such representative is available and if the research cannot be delayed, the study may proceed without informed consent provided that the specific reasons for involving subjects with a condition that renders them unable to give informed consent have been stated in the research protocol and the study has been approved by a research ethics committee. Consent to remain in the research must be obtained as soon as possible from the subject or a legally authorised representative.

31. The physician must fully inform the patient which aspects of their care are related to the research. The refusal of a patient to participate in a study or the patient's decision to withdraw from the study must never adversely affect the patient-physician relationship.

32. For medical research using identifiable human material or data, such as research on material or data contained in biobanks or similar repositories, physicians must seek informed consent for its collection, storage and/or reuse. There may be exceptional situations where consent would be impossible or impracticable to obtain for such research. In such situations the research may be done only after consideration and approval of a research ethics committee.

Use of Placebo

33. The benefits, risks, burdens and effectiveness of a new intervention must be tested against those of the best proven intervention(s), except in the following circumstances:

Where no proven intervention exists, the use of placebo, or no intervention, is acceptable; or

Where for compelling and scientifically sound methodological reasons the use of any intervention less effective than the best proven one, the use of placebo, or no intervention is necessary to determine the efficacy or safety of an intervention and the patients who receive any intervention less effective than the best proven one, placebo, or no intervention will not be subject to additional risks of serious or irreversible harm as a result of not receiving the best proven intervention.

Extreme care must be taken to avoid abuse of this option.

Post-Trial Provisions

34. In advance of a clinical trial, sponsors, researchers and host country governments should make provisions for post-trial access for all participants who still need an intervention identified as beneficial in the trial. This information must also be disclosed to participants during the informed consent process.

Research Registration and Publication and Dissemination of Results

35. Every research study involving human subjects must be registered in a publicly accessible database before recruitment of the first subject.

36. Researchers, authors, sponsors, editors and publishers all have ethical obligations with regard to the publication and dissemination of the results of research. Researchers have a duty to make publicly available the results of their research on human subjects and are accountable for the completeness and accuracy of their reports. All parties should adhere to accepted guidelines for ethical reporting. Negative and inconclusive as well as positive results must be published or otherwise made publicly available. Sources of funding, institutional affiliations and conflicts of interest must be declared in the publication. Reports of research not in accordance with the principles of this Declaration should not be accepted for publication.

Unproven Interventions in Clinical Practice

37. In the treatment of an individual patient, where proven interventions do not exist or other known interventions have been ineffective, the physician, after seeking expert advice, with informed consent from the patient or a legally authorised representative, may use an unproven intervention if in the physician's judgement it offers hope of saving life, re-establishing health or alleviating suffering. This intervention should subsequently be made the object of research, designed to evaluate its safety and efficacy. In all cases, new information must be recorded and, where appropriate, made publicly available.
